3,175 study participants total, including 2,875 participants in the stepped-wedge study (1,375 in the observation period and 1,500 in the intervention period). We estimate that approximately 2% of participants in the observation period (n=28) and approximately 5% of participants in the intervention period (n=75) will test positive for HIV infection and continue in the study. We estimate that up to 300 partners of newly diagnosed individuals will be offered enrollment and tested for HIV using standard tests (observation period) or HIV-1 RNA testing (intervention period).

Participating Sites:

KEMRI-Wellcome Trust Programme, Kilifi, Kenya (DAIDS-ES ID # 38181), with stepped wedge trial implementation at 6 community health facilities (2-4 public, 2-4 private) and ART and PrEP cohort follow-up at the nearest of our two KEMRI Research Clinics, located in Mtwapa and Kilifi, Kenya

Schedule of Procedures:

Individuals eligible for the HIV-1 RNA testing intervention will be offered enrollment when they seek care at one of the study facilities, with testing taking place on that same day. For individuals with negative test results for both acute and prevalent HIV infection, no further follow-up will occur. One 6-week follow-up visit will occur after testing for all individuals who are newly diagnosed with HIV. Procedures for the aPS intervention, the ART cohort, and the PrEP cohort are detailed in this protocol.

Study Duration:

Study enrollment will occur over 24 months. Following enrollment and study procedures (1-2 hours of time), all participants who test negative for HIV infection will have no further visits. All participants newly diagnosed with HIV will have a 6-week follow-up visit. All participants who enroll in the ART or PrEP cohort will be followed for a total of 12 months.

Intervention:

Testing for acute and prevalent HIV infection, followed by partner notification services and immediate ART (provided by the Kenya Kenyan National AIDS and STD Control Program [NASCOP]) for newly diagnosed individuals and PrEP (provided by Gilead) for uninfected partners in serodiscordant relationships.

Objectives: Primary Objective:

 HIV-1 RNA testing intervention: To conduct a proof-of-concept study to determine outcomes of a health facility-based HIV-1 RNA testing intervention to identify acute (i.e., RNA-positive, seronegative or discordant rapid test results) and prevalent (i.e., RNA-positive, seropositive) HIV infection, compared to standard care.

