11.4. Assisted Partner Services (aPS)

- 11.4.1. Observation Period Participants Diagnosed with HIV Infection (Index Cases)
 - Standard HIV care guidelines in Kenya recommend testing of partners of the index case through passive partner referral. Patients diagnosed with HIV infection during the observation period will be encouraged to refer their partners for this testing.
 - Partner outcomes will be self-reported by these patients at the 6-week follow-up visit, after which all observation period index patients will be offered standard aPS (with research staff, instead of index cases, contacting named partners), using procedures summarized in section 11.4.2. Partner outcomes among observation period participants who agree to provide names for standard aPS will be documented by study staff as described below. Of note, testing of partners of index patients diagnosed in the observation period will not include the Xpert® HIV Qual test, but will consist solely of standard HIV rapid tests conducted according to Kenyan National Guidelines.
- 11.4.2. Intervention Period Participants Diagnosed with HIV Infection (Index Cases)
 - During the intervention period, we will administer our enhanced aPS intervention to all consenting index patients on the day of diagnosis, either at the health facility where the case was diagnosed or at the nearest KEMRI Research Clinic, depending on the patient's preference.
 - Research staff will describe the rationale for providing aPS and procedures for
 having providers immediately notify partners without directly revealing the index
 patient's identity. Specifically, staff will indicate that index patients who wish to
 inform partners themselves will be allowed up to 3 days to do so, after which
 research staff will notify partners following the aPS procedures. In addition, if an
 index patient requests that a certain partner not be contacted, the research team will
 respect the patient's wish and only contact partners for whom the index patient has
 given permission.
 - We will use an assessment form adapted from [name] completed aPS study
 to identify and exclude any individual from aPS who is determined to be at high risk
 of IPV, defined as reporting IPV within the last 1 month. Of note, partner notification
 following these eligibility criteria in [name] completed trial at VCT sites in
 Kenya showed no difference in IPV in the control and intervention arms.

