 seronegative in the observation period will also be referred to local facilities for
 follow-up counseling, and will not be eligible for the PrEP cohort at the KEMRI
 Research Clinics.
- Partners of index patients newly diagnosed with acute or prevalent HIV in the intervention period will be managed as follows:
 - Any partner of an intervention period index patient who is newly diagnosed with acute or prevalent HIV infection will be invited to the nearest KEMRI Research Clinic for enrolment into the ART cohort or offered referral for HIV care, if ART cohort enrolment is declined.
 - All partners of intervention period index patients who are newly diagnosed with acute or prevalent HIV will also be offered enhanced aPS, and their partners will also be offered enhanced aPS, enabling us to thoroughly investigate local sexual networks in which recent transmission occurred.
 - Partners who are uninfected but in an ongoing partnership with any individual newly diagnosed with acute or prevalent HIV infection in the intervention period will be offered enrolment in the PrEP cohort described below.
- All partners who are newly diagnosed with HIV in either study period will be
 assessed at a 6-week follow-up visit to determine linkage to care, ART uptake and
 disclosure to partners.
- At baseline and at the 6-week visit, research staff will counsel newly diagnosed individuals to disclose their HIV status to sexual partners and potential treatment supporters, and provide referral to counseling if needed for that purpose.

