12.1.3. HIV Testing for Identified Partners in the aPS Intervention

- All identified partners of index patients diagnosed in the observation period will be tested with standard HIV rapid tests, in accordance with Kenyan guidelines.
- All identified partners of index patients diagnosed in the intervention period will undergo the same screening laboratory tests as described for HIV testing in the intervention period.

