14. SAMPLE SIZE CONSIDERATIONS

The proposed work is powered for the stepped wedge design (Figure 2). Based on our pilot work, we estimate that 50%-60% of adults aged 18-39 at the six participating facilities will be eligible for the study and approximately 50%-80% of these will accept study participation. Our preliminary data shows that approximately 2% of young adults in this age range are diagnosed with prevalent HIV-1 infection under standard care, while approximately 5% will be newly diagnosed with acute (1%) or prevalent (4%) HIV-1 infection in the intervention period. If these estimates are correct, with 1,375 subjects in the observation period and 1,500 subjects in the intervention period and a type I error probability of 0.05, assuming a coefficient of variation (k) of 0.25, we will have >90% power to reject the null hypothesis that the HIV diagnosis rates for experimental and control subjects are equal [57]. This power is more than adequate for multivariable analysis related to the testing of this null hypothesis. Because facilities will not have the laboratory capacity to diagnose HIV before seroconversion during the observation period, the base rate of AHI detection is 0, and power to detect AHI during the intervention period is >90% even if AHI prevalence is well below 1%. The table below presents power for a range of coefficients of variation and acute/prevalent HIV prevalence in the intervention period, given our chosen sample size.

Table. Power for Evaluation of Null Hypothesis that HIV Diagnosis Rates are Equal

Diagnosed HIV, Observation Period	Diagnosed HIV, Intervention Period	Kappa	Power
2.0%	5.0%	0.20	94.4%
2.0%	4.3%	0.20	82.2%
2.0%	5.0%	0.25	93.0%
2.0%	4.3%	0.25	80.0%
2.0%	5.0%	0.30	91.4%
2.0%	4.3%	0.30	77.3%
2.0%	5.0%	0.35	89.4%
2.0%	4.3%	0.35	74.6%

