15.3. Partner Testing

We will compare the following week 6 outcomes between the observation and intervention periods: (1) number of partners reported; (2) number of partners successfully contacted; (3) number of partners tested; (4) number of partners newly diagnosed with prevalent HIV

infection; (5) number of partners newly diagnosed with AHI (0 in the observation period); (6) number of HIV-infected partners newly engaged in care; (7) number of HIV-uninfected partners initiating PrEP. For PrEP cohort participants (intervention period only) we will also assess the proportion initiating PrEP by month 3 following cohort enrollment and the proportion with adherence >80%, measured by self-report or MEMS® cap at months 3 and 6 following PrEP initiation. The median, inter-quartile range, and range will be presented for each outcome in each period.

Outcomes will also be compared across study periods using Poisson GEE models with a small-sample variance correction [63]. Potential predictors, adjustment for confounding by calendar time, and interaction testing will be as described for the HIV-1 RNA testing intervention analysis above. We will also analyze local sexual network characteristics including the composition of individuals' personal sexual networks by attributes, relational type, relational timing, and relational duration. Characteristics will be compared for partners of index cases with AHI vs. prevalent HIV and for networks that include or do not include one or more AHI cases, using Pearson Chi square or Fisher exact tests for binary outcomes and non-parametric tests for continuous outcomes. We will also conduct a subset of these comparisons to the sexual networks of HIV-negative respondents provided through their CASI/CAPI data. Point estimates and standard errors for each behavioral parameter will be used to parametrize the modelling efforts described below. As above, in analyses in which multiple null hypotheses are tested, p values will be adjusted using the Holm–Bonferroni method.

15.4. Impact and Cost-Effectiveness

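### Section 15.3 compares networks with and without an AHI case without conditioning on how many members were RNA-tested, on study period or on look-back window, so its tests can reject for size-linked characteristics when AHI is unrelated to network structure

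*Combined protocol and SAP*

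**What the plan says.** Section 15.3 plans to describe local sexual networks, including "the composition of individuals' personal sexual networks by attributes, relational type, relational timing, and relational duration". It then compares these characteristics in two ways: between partners of AHI and of prevalent index cases, and between "networks that include or do not include one or more AHI cases, using Pearson Chi square or Fisher exact tests for binary outcomes", with non-parametric tests for continuous outcomes. Holm-Bonferroni is applied where several hypotheses are tested. The calendar-time and confounder adjustments in that section are written for the week-6 Poisson GEE outcomes, not for these network tests.

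Three design features decide which networks can carry the AHI label, and how large they are:

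- **Period.** Section 12.1.3 says "All identified partners of index patients diagnosed in the observation period will be tested with standard HIV rapid tests". Section 11.4.1 adds that this testing "will not include the Xpert® HIV Qual test".
- **Chain tracing.** In the intervention period, newly diagnosed partners are offered enhanced aPS in turn, "enabling us to thoroughly investigate local sexual networks in which recent transmission occurred" (section 11.4.3).
- **Look-back.** Under section 11.4.2, partners are counted over 1 year for a prevalent index case but only 3 months for an AHI index case.

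Section 15.3 does not say whether observation-period networks enter the comparison. It does not mention the number of members tested or the differing windows.

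**The concern.** Chi-square, Fisher and rank tests take the group label as exchangeable between networks under the null. Here it is not. More tested members mean more chances of at least one acute result, so the label is tied to network size even if AHI falls at random. Any characteristic that also grows with size inherits the association: a partner count, an any-partner-of-this-type indicator, or concurrency, which needs at least two partners and belongs to the relational timing that section 15.3 names.

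At stake is the interpretation of a secondary analysis. An artefact of how many people were tested, or of how far back partners were counted, could be reported as a feature of networks in which acute infection occurs.

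**Working it through.** **Inputs from the documents.** 75 intervention and 28 observation index cases (Protocol Summary). Acute 1% out of 5% diagnosed, so 1/5 = 20% of index cases, or 15 of 75 (section 14). Partner HIV prevalence 48% (sections 6.4.4 and 14). Tested partners per index: 1.67 × 0.69 = 1.15 from the earlier aPS trial (section 6.4.4), or 150/75 = 2.0 from section 14. Section 14 gives "a type I error probability of 0.05" for the primary test; I use 0.05 two-sided.

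**Assumptions, not in the documents.** Acute share *s* among infected partners (5% to 20%); spread of partner numbers (Poisson, or negative binomial with dispersion 1); share of 12-month partners that fall within 3 months; partner numbers in observation networks. A network is taken as an index case plus tested partners, one tracing wave.

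**1. The plan's nearest figure.** None is given for the network comparison. Section 14 states 80% power for a relative risk of 1.58 in 30 partners of AHI cases against 120 of prevalent cases. With 0.48 against 0.48 × 1.58 = 0.758, two-sided 0.05, I get 80.8%, which agrees.

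**2. Chance of the label.** With *m* tested partners, P = 1 − 0.8 × (1 − *q*)^*m*, where *q* = 0.48 × *s*.

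| *m* | *s* = 5% (*q* = 0.024) | *s* = 20% (*q* = 0.096) |
|---|---|---|
| 0 | 20% | 20% |
| 2 | 24% | 35% |
| 8 | 34% | 64% |

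**3. Null rejection, 75 intervention networks, acute status random, nominal 5%, no look-back difference.**

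- Partner count, *s* = 5%: about 6-13%.
- Partner count, *s* = 20%: 27% (Poisson) and 43% (overdispersed) at mean 1.15; 36% and 66% at mean 2.0.
- Concurrency indicator (assumed 50% chance per additional partner), *s* = 20%: 13-25% at mean 1.15 and 17-42% at mean 2.0.
- Any partner with a trait held by 30% of partners, mean 1.67: 7-12% at *q* = 0.05 and 11-27% at *q* = 0.10.
- Proportion of partners with that trait, mean 1.67: 4-6% throughout.

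**4. Adding 28 observation networks** (Poisson, intervention mean 1.67, partner count).

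| Observation mean | *q* = 0 | *q* = 0.05 |
|---|---|---|
| 1.67 | 5% | 15% |
| 1.0 | 10% | 36% |
| 0.5 | 19% | 59% |

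At equal size the structural zero alone adds nothing. It adds error when the characteristic differs by period.

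**5. Look-back** (intervention networks only, negative binomial, mean 1.67, partner count).

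| Share of 12-month partners within 3 months | Rejection, *q* = 0 | Rejection, *q* = 0.05 | Mean partners at *q* = 0.05, labelled vs not |
|---|---|---|---|
| 1.0 | 5% | 25% | 2.24 vs 1.46 |
| 0.5 | 29% | 6% | 1.62 vs 1.46 |
| 0.25 | 76% | 14% | 1.29 vs 1.47 |

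The shorter window alone produces false rejection. Combined with the size effect it can cancel it or reverse its sign.

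**6. Does conditioning work?** Shuffling acute status within index cases and within tested partners, with network sizes fixed and one window for all, rejects in 3.7-6.4% of runs for partner count and 3.7-4.8% for the any-partner indicator. Shuffling among diagnosed members only gives 4-7%. With the unequal windows left in place and half of 12-month partners falling within 3 months, a fixed-size permutation rejects in about 10-52%. The common window must therefore come first.

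**The case against.** Several stronger readings are tempting, and the documents do not support them.

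- *These tests reject too often in general.* They do not. Section 15.3 names composition, type, timing and duration, not partner count, and proportions hold their level. However, its list is not closed, and concurrency is size-linked.
- *20% acute among partners is the plan's figure.* It is not. The 1% and 5% describe trial participants selected by an AHI risk score; partners are not scored. At a 5% share the inflation is modest.
- *Observation networks are pooled.* Section 15.3 does not say so. It also does not exclude them.
- *AHI networks will look larger.* The 3-month window pulls the other way, so this cannot be claimed.
- *The result would wrongly confirm the local-outbreak hypothesis in section 6.3.* That hypothesis concerns additional cases found through aPS, which this test does not assess. The transmission model takes point estimates and standard errors, not these p-values.

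Holm-Bonferroni is a fair reply only in part. At the first step for four characteristics (0.05/4 = 0.0125) the 27% case falls to 12%, still 12/1.25 = 9.6 times that threshold. The adjustment handles multiplicity, not a null that fails by construction. Nor is the look-back a defence: it is a second artefact, and cancellation would be coincidental.

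**Conclusion.** The concern holds for size-linked characteristics. With 75 networks and 20% of index cases acute, null rejection for partner count is about 6-13% if 5% of infected partners are acute and about 27-66% if 20% are, before any look-back effect. Proportions stay near 5%. These figures rest on an assumed partner acute share, an assumed spread of partner numbers, and acute status independent between members. Observation-period networks, if included, add bias when tracing or network features differ by period. The unequal look-back makes AHI-index networks smaller and leaves the net direction unknown. This is a secondary comparison and the primary analysis is unaffected, but the wording should be corrected before the data are analysed.

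**What to change.** In section 15.3:

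- **(a)** Restrict the AHI-network comparison to networks of intervention-period index cases whose members were RNA-tested.
- **(b)** For this comparison only, define network characteristics from partners in the past 3 months for every index case. Partner elicitation for tracing is not affected.
- **(c)** On that common-window network, condition on the number of members tested or diagnosed. One way is to permute acute/prevalent status among diagnosed, RNA-tested members, stratified by index versus partner, with each network's diagnosed count held fixed, and to recompute the label at each shuffle.

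Section 11.4.3 and footnote 2 of Appendix 21.3 also need reconciling. The first sends home-collected blood from intervention-period partners for the RNA test; the second lists only rapid tests when partners are tested at home. This decides which members can be labelled acute.

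The cost is a few sentences of plan text and a short permutation program, with no new data. Observation-period networks and partners from more than 3 months ago leave this one comparison. The former carry no information on AHI; losing the latter costs some precision.

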15.5. Barriers and Facilitators

For newly diagnosed patients or uninfected partners who decline cohort enrolment but consent to an in-depth interview, we will conduct a single interview. For those who enroll in the ART or PrEP cohorts, we will aim to conduct four in-depth interviews per interviewee. The first one will take place approximately 2 weeks after diagnosis of acute or prevalent HIV infection or confirmation of uninfected status in an ongoing discordant partnership. Subsequent interviews will take place at months 3, 6, 9, and 12, coinciding with cohort follow-up visits. A grounded theory framework will be used for analysis. Audio recordings of the in-depth interviews will be transcribed verbatim; identifying information will be omitted from transcripts. Transcribed interviews will be entered into NVivo, and analysis will aim to identify and categorize the attitudinal, psychosocial, and contextual factors associated with ART or PrEP use. Data analysis will be iterative, and include open coding, axial coding, marginal remarks, comparisons, and memo-writing. Themes will be analyzed and triangulated. The next stage of analysis will relate concepts in order to identify factors that can enhance quality of health services and counselling for HIV-infected patients and their partners. Data will be collected confidentially, secured and stored in study offices. Audio recordings of the interviews will be destroyed after transcription. Personally identifiable information opinions and quotations will not be used in publications arising from this work.

15.6. Views of Health Facility Staff

We aim to conduct in-depth interviews or focus group discussions for up to 60 staff at the 6 health facilities (i.e., up to 10 staff members per facility) at which our HIV-1 RNA testing intervention will take place. These interviews or discussions will take place before and after each facility's participation in the intervention phase of this study, in order to get staff views of the importance of early detection of HIV infection, the impact this research had on the facility in general, and any challenges that were encountered that might make scale-up difficult. As for participant interviews, a grounded theory framework will be used for analysis. Audio recordings of the in-depth interviews and focus group discussions will be transcribed verbatim; identifying information will be omitted from transcripts. Transcribed interviews and focus group discussions will be entered into NVivo, and analysis will aim to identify and categorize knowledge, attitudes, and contextual factors associated with the HIV-1 RNA testing intervention evaluated. Data analysis will be iterative, and include open coding, axial coding, marginal remarks, comparisons, and memo-writing. Themes will be analyzed and triangulated. The next stage of analysis will relate concepts in order to identify factors that can enhance uptake of the HIV-1 RNA testing intervention at similar health facilities around Kenya. Data

Novel HIV-1 RNA testing intervention to detect acute and prevalent HIV infection – Tambua Mapema Plus

will be collected confidentially, secured and stored in study offices. Audio recordings of the interviews and focus group discussions will be destroyed after transcription. Personally identifiable information opinions and quotations will not be used in publications arising from this work.

Version 1.1 17 July 2018 Page **63** of **137**

16. DATA MANAGEMENT

16.1. Data Management Responsibilities

- Source data/documents will be maintained in accordance with Requirements for Source Documentation in DAIDS Funded and/or Sponsored Clinical Trials at https://www.niaid.nih.gov/sites/default/files/sourcedocappndx.pdf.
- The investigators will maintain and store securely complete, accurate and current study
 records on site throughout study implementation. Study records will be retained for at
 least 3 years after the research is completed, in compliance with DAIDS policy of storage
 and retention of clinical records. No study records may be moved to an off-site location
 or destroyed prior to receiving approval from both DAIDS and the Sponsor.

